Appendix 1B: 1996 Version of Declaration of Helsinki

World Medical Association Declaration of Helsinki: Recommendations Guiding Medical Doctors in Biomedical Research Involving Human Subjects

Adopted by the 18th World Medical Assembly, Helsinki, Finland, June 1964 and amended by the 29th World Medical Assembly, Tokyo, Japan, October 1975, 35th World Medical Assembly, Venice, Italy, October 1983, 41st World Medical Assembly, Hong Kong, September 1989, and the 48th General Assembly, Somerset West, Republic of South Africa, October 1996

INTRODUCTION

It is the mission of the physician to safeguard the health of the people. His or her knowledge and conscience are dedicated the fulfilment of this mission. The Declaration of Geneva of the World Medical Assembly binds the physician with the words, "The health of my patient will be my first consideration," and the International Code of Medical Ethics declares that, "A physician shall act only in the patient's interest when providing medical care which might have the effect of weakening the physical and mental condition of the patient."

The purpose of biomedical research involving human subjects must be to improve diagnostic, therapeutic and prophylactic procedures and the understanding of the aetiology and pathogenesis of disease.

In current medical practice most diagnostic, therapeutic or prophylactic procedures involve hazards. This applies especially to biomedical research. Medical progress is based on research which ultimately must rest in part on experimentation involving human subjects.

In the field of biomedical research a fundamental distinction must be recognized between medical research in which the aim is essentially diagnostic or therapeutic for a patient, and medical research, the essential object of which is purely scientific and without implying direct diagnostic or therapeutic value to the person subjected to the research.

Special caution must be exercised in the conduct of research which may affect the environment, and the welfare of animals used for research must be respected.

Because it is essential that the results of laboratory experiments be applied to human beings to further scientific knowledge and to help suffering humanity, the World Medical Association has prepared the following recommendations as a guide to every physician in biomedical research involving human subjects. They should be kept under review in the future. It must be stressed that the standards as drafted are only a guide to physicians all over the world. Physicians are not relieved from criminal, civic and ethical responsibilities under the laws of their own countries.

I. BASIC PRINCIPLES

1. Biomedical research involving human subjects must conform to generally accepted scientific principles and should be based on adequately performed laboratory and animal experimentation and on a thorough knowledge of the scientific literature.

2. The design and performance of each experimental procedure involving human subjects should be clearly formulated in an experimental protocol which should be transmitted for consideration, comment and guidance to a specially appointed committee independent of the investigator and the sponsor provided that this independent committee is in conformity with the laws and regulations of the country in which the research experiment is performed.
3. Biomedical research involving human subjects should be conducted only by scientifically qualified persons and under the supervision of a clinically competent medical person. The responsibility for the human subject must always rest with a medically qualified person and never rest on the subject of the research, even though the subject has given his or her consent.
4. Biomedical research involving human subjects cannot legitimately be carried out unless the importance of the objective is in proportion to the inherent risk to the subject.
5. Every biomedical research involving human subjects should be preceded by careful assessment of predictable risks in comparison with foreseeable benefits to the subject or to others. Concern for the interest of the subject must always prevail over the interests of science and society.
6. The right of the research subject to safeguard his or her integrity must always be respected. Every precaution should be taken to respect the privacy of the subject and to minimize the impact of the study on the subject's physical and mental integrity and on the personality of the subject.
7. Physicians should abstain from engaging in research projects involving human subjects unless they are satisfied that the hazards involved are believed to be predictable. Physicians should cease any investigation if the hazards are found to outweigh the potential benefits.
8. In publication of the results of his or her research, the physician is obliged to preserve the accuracy of the results. Reports of experimentation not in accordance with the principles laid down in this Declaration should not be accepted for publication.
9. In any research on human beings, each potential subject must be adequately informed of the aims, methods, anticipated benefits and potential hazards of the study and the discomfort it may entail. He or she should be informed that he or she is a liberty to abstain from participation in the study and that he or she is free to withdraw his or her consent to participation at any time. The physician should then obtain the subject's freely-given informed consent, preferably in writing.
10. When obtaining informed consent for the research project the physician should be particularly cautious if the subject is in a dependent relationship to him or her or may consent under duress. In that case the informed consent should be obtained by a physician who is not engaged in the investigation and who is completely independent of this official relationship.
11. In case of legal incompetence, informed consent should be obtained from the legal guardian in accordance with national legislation. Where physical or mental incapacity makes it impossible to obtain informed consent, or when the subject is a minor, permission from the responsible relative replaces that of the subject in accordance with national legislation.

Whenever the minor child is in fact able to give consent, the minor's consent must be obtained in addition to the consent of the minor's legal guardian.

12. The research protocol should always contain a statement of the ethical considerations involved and should indicate that the principles enunciated in the present Declaration are complied with.

II. MEDICAL RESEARCH COMBINED WITH CLINICAL CARE (Clinical research)

1. In the treatment of the sick person, the physician must be free to use a new diagnostic and therapeutic measure, if in his or her judgement it offers hope of saving life, reestablishing health or alleviating suffering.
2. The potential benefits, hazards and discomfort of a new method should be weighed against the advantages of the best current diagnostic and therapeutic methods.
3. In any medical study, every patient -- including those of a control group, if any -- should be assured of the best proven diagnostic and therapeutic method. This does not exclude the use of inert placebo in studies where no proven diagnostic or therapeutic method exists.
4. The refusal of the patient to participate in a study must never interfere with the physician-patient relationship.
5. If the physician considers it essential not to obtain informed consent, the specific reasons for this proposal should be stated in the experimental protocol for transmission to the independent committee (I,2).
6. The physician can combine medical research with professional care, the objective being the acquisition of new medical knowledge, only to the extent that medical research is justified by its potential diagnostic or therapeutic value for the patient.

III. NON-THERAPEUTIC BIOMEDICAL RESEARCH INVOLVING HUMAN SUBJECTS (Non-clinical biomedical research)

1. In the purely scientific application of medical research carried out on a human being, it is the duty of the physician to remain the protector of the life and health of that person on whom biomedical research is being carried out.
2. The subject should be volunteers - either healthy persons or patients for whom the experimental design is not related to the patient's illness.
3. The investigator or the investigating team should discontinue the research if in his/her or their judgement it may, if continued, be harmful to the individual.
4. In research on man, the interest of science and society should never take precedence over considerations related to the well being of the subject.

Amend. 1, 19Jan2016; Amend. 2, 18May2016; Amend. 3, 21Oct2016; Amend. 4, 03Mar2017; Amend. 5, 29Mar2017; Amend. 6, 13Apr2017; Amend. 7, 02Oct2017; Amend. 8, 02Nov2017; Amend. 9, 11Feb2018; Amend. 10, 29Nov2018; Amend. 13, 10Dec2019; Amendment 14, 17 March 2020, Clean, Final

19.2 APPENDIX 2: Clinically Notable Values

The following guidelines, originally established by the Division of Neuropharmacological Drug Products of the FDA, will be used for determining clinically notable values for laboratory and vital signs parameters.

NOTABLE VALUES FOR LABORATORY PARAMETERS AND VITAL SIGNS

CLINICALLY NOTABLE BLOOD CHEMISTRY VALUES

Parameter	Synonym	S.I. units			Other units		
		Unit	Lower Limit	Upper Limit	Unit	Lower Limit	Upper Limit
Albumin		g/L	≤ 14	≥ 62	g/dL	≤ 1.4	≥ 6.2
Alk. Phosphatase	ALP	U/L	NA	≥ 3.0*URL			
Amylase		U/L	≤ 15	≥ 350			
ALAT, SGPT	ALT,GPT	U/L	NA	≥ 3.0*URL			
ASAT, SGOT	AST,GOT	U/L	NA	≥ 3.0*URL			
Bicarbonate		mmol/L	≤ 10	NA			
Bilirubin total		μmol/L	NA	≥ 34	mg/dL		≥ 2.0
Calcium total		mmol/L	≤ 2.1	≥ 3.0	mg/dL	≤ 8.2	≥ 12
Chloride		mmol/L	≤ 80	≥ 125			
Cholesterol		mmol/L	NA	≥ 141	mg/dL		≥ 500
Creatinine kinase	CPK	U/L	NA	≥ 3.0*URL			
Creatinine		μmol/L	NA	≥ 177	mg/dL		≥ 2.0
Gamma-GT Male		U/L	NA	≥ 100			
Female		U/L	NA	≥ 90			
Globulin total		g/L	≤ 10	NA			
Glucose		mmol/L	≤ 1.7	≥ 13.9	mg/dL	≤ 30	≥ 250
LDH		U/L	NA	≥ 3.0*URL			
Phosphate		mmol/l	NA	≥ 2			
Potassium		mmol/L	≤ 2.5	≥ 6.5			
Protein total		g/L	≤ 45	NA			
PTT		sec	NA	≥ 80			
Sodium		mmol/L	≤ 120	≥ 165			
Triglycerides		mmol/L	NA	≥ 5.6	mg/dL		≥ 500
Urea		mmol/L	NA	≥ 16.6	mg/dL		≥ 100
Urea nitrogen	BUN	mmol/L	NA	≥ 84.0	mg/dL		≥ 30
Uric acid Male		μmol/L	NA	≥ 624	mg/dL		≥ 10.5
Female		μmol/L	NA	≥ 505	mg/dL		≥ 8.5

Amend. 1, 19Jan2016; Amend. 2, 18May2016; Amend. 3, 21Oct2016; Amend. 4, 03Mar2017; Amend. 5, 29Mar2017; Amend. 6, 13Apr2017; Amend. 7, 02Oct2017; Amend. 8, 02Nov2017; Amend. 9, 11Feb2018; Amend. 10, 29Nov2018; Amend. 13, 10Dec2019; Amendment 14, 17 March 2020, Clean, Final

CLINICALLY NOTABLE HEMATOLOGY VALUES

Parameter	Synonym	S.I. units			Other units		
		Unit	Lower Limit	Upper Limit	Unit	Lower Limit	Upper Limit
Basophils		L/L	NA	≥ 0.15	%		≥ 15
Eosinophils		L/L	NA	≥ 0.10	%		≥ 10
Erythrocytes	RBC	10 ¹² /L	≤ 2.5	NA			
	Female	10 ¹² /L	≤ 2.0	NA			
ESR	Male	Mm	NA	≥ 25			
	Female	Mm	NA	≥ 35			
Hematocrit	Male	EVF	L/L	≤ 0.37	NA	%	≤ 37
	Female		L/L	≤ 0.32	NA	%	≤ 32
Hemoglobin	Male		g/L	≤ 115	NA	g/dL	≤ 11.5
	Female		g/L	≤ 95	NA	g/dL	≤ 9.5
Leukocytes	WBC	10 ⁹ /L	≤ 2.8	≥ 16.0			
Lymphocytes		L/L	NA	≥ 0.80	%		≥ 80
MCHC		mmol/L	≤ 12.4	≥ 27.9	g/dL	≤ 20	≥ 45
MCV		10 ⁻¹⁵ L	≤ 60	≥ 120			
Monocytes		L/L	NA	≥ 0.40	%		≥ 40
Neutrophils		L/L	≤ 0.15	NA	%	≤ 15	
Thrombocytes	Platelets	10 ⁹ /L	≤ 75	≥ 700			

CLINICALLY NOTABLE URINALYSIS VALUES

Variable	Clinically Notable Values
Protein	Increase of 2 units
Glucose	Increase of 2 units

CLINICALLY NOTABLE VITAL SIGNS VALUES

Parameter	Unit	Decrease	Increase
Sitting/Supine SBP	mmHg	Value ≤ 90 and ≥ 20 decrease from Baseline.	Value ≥ 180 and ≥ 20 increase from Baseline
Sitting/Supine DBP	mmHg	Value ≤ 50 and ≥ 15 decrease from Baseline.	Value ≥ 105 and ≥ 15 increase from Baseline
Orthostatic Hypotension (based on standing SBP/DBP)	mmHg	Decrease in SBP/DBP from Supine to Standing position exceeding > 30mmHg	NA
Sitting pulse rate	bpm	Value ≤ 50 and ≥ 15 decrease from Baseline	Value ≥ 120 and ≥ 15 increase from Baseline
Weight	kg	≥ 7% decrease from Baseline.	≥ 7% increase from Baseline.
Respiration rates*	Breaths/minute	< 12	> 25
Temperature	°C	NA	Value ≥ 38.3 and ≥ 1.1 increase from Baseline.
Temperature	°F	NA	Value ≥ 101.0 and ≥ 2.0 increase from baseline

* For respiration rate values are relevant, not decrease/increase.

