Two sarizotan *dose-range-finding studies* conducted in juvenile rats, an initial study ([ONP0106](#)) in which treatment started in 21-day old pups (corresponding to a 2-year old child), and a 2nd study ([ONP0113](#)) in 7-day old pups (corresponding to a newly born child), indicated the presence of effects on body weight, and relatively severe CNS signs in the 7-day old pups, thus limiting the *main study* (YG47PW) to be performed in 21-day old pups, at doses of 0, 12.5, 25 and 50 mg/kg/day. In this study, at the 50 mg/kg dose, a treatment-related death was observed, as well as CNS signs (underactive behavior, flat posture, piloerection, and splayed limbs); similar signs, but of a lower severity, were encountered in all dose groups (including 12.5 and 25 mg/kg), which resolved during the day. In addition, reduced ulnar growth (50 mg/kg), abnormalities in weight gain (50 mg/kg males, all groups females), oestrus irregularity (all groups), delay in reproductive maturity (50 mg/kg), abnormalities in motor activity (50 mg/kg) and during the functional operational battery (FOB) (all groups), and impairments in learning and memory (all groups) were noted. All of the above changes showed recovery, apart from the increase in motor activity. Despite treatment-related histopathological changes (large corpora lutea, vaginal dioestrus, mammary gland hypertrophy/hyperplasia, and adrenal gland zona glomerulosa hypertrophy) during treatment, there was no difference between sarizotan and placebo-treated animals during recovery. There was no evidence of an effect of any of the doses on mating behavior, pregnancy, conception and fertility indices, or the number of live embryos or litter size.

Amend. 1, 19Jan2016; Amend. 2, 18May2016; Amend. 3, 21Oct2016; Amend. 4, 03Mar2017; Amend. 5, 29Mar2017; Amend. 6, 13Apr2017; Amend. 7, 02Oct2017; Amend. 8, 02Nov2017; Amend. 9, 11Feb2018; Amend. 10, 29Nov2018; Amend. 13, 10Dec2019; Amendment 14, 17 March 2020, Clean, Final

The Functional Observational Battery (FOB) revealed an increase in vocalisation, particularly in females, in all treated groups during the in-hand observations, and an increase in the incidence of flattened posture, abnormal gait, tremors, urination and defecation, and a decrease in the levels of arousal and rearing during the 2-minute arena observation. All arena counts, except high urination and fecal counts, showed full recovery.

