No PK data has been collected previously for sarizotan in pediatric patients or patients with RTT; therefore, blood samples will be collected in this study for measurement of sarizotan. However, due to the small size and fragile nature of RTT patients, PK sampling in this study will be limited to samples taken pre-dose and 1 and 4 hours post-dose for the initial dose (Dose Level 1) on Day 1, and the morning dose at Dose Level 4 on Day 15. In adults, sarizotan had a rapid T_{max} of ~1 hr and a relatively short terminal elimination half-life of 5-7 hr (see [Section 7.1.3](#)). Therefore, if metabolism in these RTT patients is similar to adults, these sampling times should capture the post-dose peak concentration and the initial tail of the curve.

Rationale for choice of patient population

To be eligible for the study patients must have a diagnosis of RTT based on consensus clinical criteria ([Neul et al, 2010](#); [Appendix 4](#)); a test for MECP2 mutations (Xq28) will be performed, but is not required for the diagnosis. The selected population for this first study will include patients 4 years of age or older, and weighing at least 10 kg ([Tarquinio et al, 2102](#)). As shown in a recent study ([Mackay et al, 2017](#)), autonomic breathing abnormalities, including breath-holding and hyperventilation, have been observed in a substantial proportion of RTT patients below the age of 6 years. Dosing of patients as young as 4 years of age is supported by the results of a recently completed juvenile toxicity study performed in 21-day old rats (see [Section 7.1.2](#)).

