12.1.2 Vital Signs

Vital signs assessments will be performed at all scheduled evaluations (Tables 6A, 6B, 6C, 6D and 6E). Vital signs will include, body weight, temperature, pulse, systolic and diastolic blood pressure, and respiratory rate. Pulse and blood pressure will be measured after the subject has been resting for at least 5 minutes. At the baseline visit, on Day 0 or at least 1 hour prior to the first dose of study medication on Day 1, measurements of blood pressure and pulse will be repeated 3 times, at least 10 minutes apart, and the values will be averaged to obtain the baseline values. In addition, height will be measured at Screening and Baseline, and at 8-week or 12-week intervals throughout the study.

In the extension treatment period, vital signs assessments will be performed prior to the first dose of study medication on Day 168 (final Week 24 assessment from the double-blind period), and repeated at 1 and 4 hours post-dose. Similarly, pre- and post-dose assessments will be performed on Day 196 (Week 28) for the first administration of the target dose (10 mg *bid*).

Amend. 1, 19Jan2016; Amend. 2, 18May2016; Amend. 3, 21Oct2016; Amend. 4, 03Mar2017; Amend. 5, 29Mar2017; Amend. 6, 13Apr2017; Amend. 7, 02Oct2017; Amend. 8, 02Nov2017; Amend. 9, 11Feb2018; Amend. 10, 29Nov2018; Amend. 13, 10Dec2019; Amendment 14, 17 March 2020, Clean, Final

If a change of *clinical relevance* from pre-dose to post-dose is observed, the vital signs assessment should be repeated as often as needed, at the discretion of the Investigator. Findings should be documented on the Vital Signs section of the Case Report Form.

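### The clinically notable limits for vital signs have no age or growth adjustment in a trial that enrols from age 4: the high-pressure flag is insensitive in children, the weight flag misses stalled growth, and the orthostatic row has no planned measurement.

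*Protocol*

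**What the plan says.** Protocol section 19.2 (Appendix 2) gives a single table of clinically notable vital signs, taken from general FDA division guidelines, and SAP Appendix 3 repeats it. Three rows matter here:

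- **Weight:** a fall of at least 7%, or a rise of at least that size ("7% increase from Baseline").
- **High blood pressure:** systolic "Value ≥ 180 and ≥ 20 increase from Baseline"; diastolic "Value ≥ 105 and ≥ 15 increase from Baseline".
- **Orthostatic hypotension:** "Decrease in SBP/DBP from Supine to Standing position exceeding > 30mmHg".

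No row depends on age. On eligibility, Protocol section 7.3 states: "The selected population for this first study will include patients 4 years of age or older, and weighing at least 10 kg". There is no upper age limit.

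On measurement, Protocol section 12.1.2 says: "Pulse and blood pressure will be measured after the subject has been resting for at least 5 minutes". Weight is taken at scheduled visits and height every 8 or 12 weeks.

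On reporting, SAP section 17.5 plans an incidence table of notable vital signs at Day 1, Day 15, Week 24 and end of study, and refers to Appendix 3 for the limits. Its list of vital signs to be reported has systolic and diastolic pressure, pulse, respiratory rate and temperature, but not weight. The SAP covers the double-blind period only. Protocol section 15.2.5 identifies notable values in both periods and resets the baseline at Week 24 for the extension.

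**The concern.** A patient-level flag should pick out the patients in whom something unusual happened. Fixed limits can fail to do that in a child. An absolute pressure floor may be far above anything a small child approaches. A percentage weight limit mixes growth with drug effect. An orthostatic rule needs two postures.

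The stakes are those of a first paediatric exposure. Section 7.3 says the drug has not been given to children before. Section 7.1.2 reports from the main juvenile rat study "abnormalities in weight gain (50 mg/kg males, all groups females" as well as reduced ulnar growth at the top dose, and adds that these changes recovered. The weight question of interest is therefore whether children on drug gain less than they should, and the rule as written does not ask it. An empty orthostatic row could also be read as no cases when it means that nobody was assessed.

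**Working it through.** The plan states no figure for how often these flags should occur, so there is nothing to reproduce. The check is threshold arithmetic.

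**High blood pressure.** Rise needed = the larger of (limit − baseline) and the stated minimum change.

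- The change condition decides only if baseline exceeds 180 − 20 = 160 systolic, or 105 − 15 = 90 diastolic.
- The documents give no childhood pressures. Assume systolic 90 to 110 mmHg: 180 − 110 = 70 and 180 − 90 = 90, which is 3.5 to 4.5 times the stated 20.
- Assume diastolic 50 to 70 mmHg: 105 − 70 = 35 and 105 − 50 = 55, against a stated 15.

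**Weight: growth needed to reach +7%.** With t in years, the annual rate needed is 7/t (linear) or 1.07^(1/t) − 1 (compound).

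- 24 weeks, t = 0.46: 15.2% or 15.9% a year.
- 168 weeks, t = 3.22: 2.2% or 2.1% a year.
- In kilograms, 7% is 0.70 at 10 kg, 1.26 at 18 kg and 1.75 at 25 kg.

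**Weight: share flagged.** The documents give neither growth rates nor the spread of weight change, so both are assumed. Mean gain = (1 + g)^t − 1. Weeks to +7% = ln 1.07 / ln(1 + g) × 52.18. Chance of a flag = 1 − Φ((7 − mean gain)/SD), with SD 1.5 to 3%.

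| Growth per year | Mean gain, 24 weeks | Weeks to +7% | Flagged at Week 24 | Mean gain, 168 weeks |
|---|---|---|---|---|
| 5% | 2.3% | 72 | 0.1–6% | 17% |
| 8% | 3.6% | 46 | 1–13% | 28% |
| 10% | 4.5% | 37 | 5–20% | 36% |
| 12% | 5.4% | 31 | 14–29% | 44% |
| 15% | 6.6% | 25 | 40–45% | 57% |

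A wider assumed SD of 3 to 4% with 6 to 14% a year gives mean gains of 6 × 24/52 = 2.8% to 14 × 24/52 = 6.5%, and 8 to 45% flagged at Week 24. At 168 weeks practically every child growing 5% a year or more is over the limit. A patient with no growth has a 0 to 1% chance.

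**Weight: stalled growth.** A child who stops growing has a change of 0% and meets neither limb. At an expected gain of 2.8 to 6.5%, the fall rule is reached only when the child is 7 + 2.8 = 9.8 to 7 + 6.5 = 13.5 percentage points of baseline weight behind expectation at Week 24.

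**Weight in the SAP.** Section 17.5 lists five vital signs without weight, yet sends the reader to an appendix with a weight row. Either the weight flag is tabulated as it stands, or weight is not summarised at all.

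**Orthostatic row.** It needs a supine and a standing reading. Section 12.1.2, the schedule in Table 6A, the visit lists in section 11.4 and SAP section 17.5 specify no such pair. The row cannot be evaluated from the planned data.

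**The case against.** The opposing case is substantial, and much of it stands.

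- **The 24-week period is controlled.** At 6 to 14% a year mean growth stays below 7%, so the share flagged depends on the assumed SD. Flags from growth should arise in all arms. This stands. It does not rescue the rule for stalled growth: if the drug slowed growth, the sarizotan arms could show fewer notable weights than placebo.
- **A reader might infer that the SAP will tabulate all three rules.** Section 17.5 does not support that for weight, because weight is not among the vital signs it reports.
- **A reader might infer that growth failure or large pressure rises would go unseen.** The documents do not support that. Pressure is summarised as actual value and change by visit and timepoint and listed by patient, weight and height are collected, investigators repeat vital signs after a relevant post-dose change, and the safety board receives vital signs data.
- **The orthostatic row may be a dormant template row.** The protocol's table also holds amylase, PTT, uric acid, phosphate and ESR, which are not among the planned tests in Table 7. That is plausible, and the table shells and case report form are not available here. It supports tidying the table.
- **The childhood pressures are assumptions, and an extreme limit can be a deliberate choice.** True. However, the finding that the change condition decides only above 160/90 needs no assumed baseline.

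**Conclusion.** The point holds as a mis-specification of the flags for children. A reader might go further and infer that the rules fail throughout the trial. The documents do not support that: there is no upper age limit, patients who have stopped growing are largely unaffected, and the low-pressure rules still operate. The fall-in-weight rule also still operates, although growth can mask a loss.

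What rests on the documents alone: the limits are unadjusted from age 4; the pressure-change condition decides only above a baseline of 160/90; a child with no weight change is not flagged; the SAP defines a notable weight change but does not list weight for reporting; and no supine and standing pair is scheduled.

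What follows by arithmetic from the plan's durations: growth alone reaches +7% in 24 weeks only at about 15% a year, but in the uncontrolled 168-week extension anything above about 2.1% a year is enough. The weight flag loses most of its meaning there for growing patients.

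What rests on assumptions: the 70 to 90 mmHg rise (systolic baseline 90 to 110) and every share flagged at Week 24 (growth rate and SD). The point should be acted on because correction is cheap and the population is newly exposed, but it touches safety reporting and not the efficacy conclusions.

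**What to change.** All changes concern reporting flags. None alters treatment or adds a measurement.

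1. **Weight.** Add weight to the SAP section 17.5 summaries, so that it agrees with Appendix 3. For growing patients, report change in weight-for-age z-score and flag falls. Use the Rett-specific growth paper that both documents cite if it supplies the parameters, and otherwise another stated reference. Do the same in the open-label SAP still to be written, where the need is greatest.
2. **High blood pressure.** For children, replace the 180/105 floor in the incidence table with a published age-specific upper limit chosen by the sponsor, and keep the existing rise from baseline.
3. **Orthostatic row.** Delete it, or report it as not assessed.

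The cost is loading the reference tables, some derivation programming, and aligning Protocol Appendix 2 with SAP Appendix 3. The two tables of notable values already differ in one place: the total cholesterol limit is 500 mg/dL in the protocol and 280 mg/dL in SAP Appendix 2.
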